The rationale for using proton beam radiotherapy is the superior dose distribution that can be achieved in comparison with photon-based techniques. Protons and other charged particles deposit little energy in tissue until near the end of the proton range; there, the residual energy is lost over a short distance, resulting in a steep rise in the absorbed dose known as the Bragg peak. Proton dose distributions are characterized by a lower-dose region in normal tissue proximal to tumor, a uniform high-dose region in the tumor, and zero dose beyond the tumor.¹⁸⁻²⁰ Also, IMRT treatment plans often include localized areas within the high-dose volumes where dose inhomogeneity can be as high as 15-20% above the target dose. Depending on the location of these “hot spots,” there can be unanticipated acute normal-tissue toxicity.²¹ Whether there are late effects attributable to these focal hot spots is unclear. Proton dose distributions are generally more homogenous. The dosimetric advantage of proton radiotherapy may translate into improved acute and late effects due to improved normal-tissue sparing in the treatment of extremity and truncal soft tissue sarcoma. However, these potential advantages need to be validated in clinical trials.

We propose a phase II study to evaluate the effect of preoperative proton radiotherapy on the reduction of late radiation morbidity, patterns of failure, local failure rate, and impact of late radiation morbidity on general quality of life (QOL).

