7.0 Patient Assessments

7.1 – Study Parameters

	Pre-TX	Weekly during Proton treatment	Post Proton treatment prior to surgery	Q3 months in years 1-2 after surgery and/or postoperative proton therapy, then Q6 months in year 3-6
Pathologically confirmed dx	X			
History/Physical exam with weight	X	X	X	X
MRI and/or CT with contrast of tumor	X		X Can be either MRI or CT	Q6 months in years 1-2, then annually (either MRI or CT)
CT of chest	X			Q6 months in years 1-2, then annually
CT of abdomen & pelvis	X			
Performance status	X	X	X	X
CBC w/ diff & ANC	X			
Pregnancy test (if applicable)	X			
Thyroid function test	X If thyroid in RT field			
MSTS	X			At 12, 18, and 24 months from start of proton treatment
FACT-G	X			At 12, 18, and 24 months from start of proton treatment
Toxicity assessment		X	X	X

7.2 Pretreatment evaluation – see table above and section 3.0 for all pretreatment assessments

7.2.1 – The physician or designee will complete the Musculoskeletal Tumor Rating Scale (MSTS) prior to treatment (see Section 7.8)

7.2.2 – The patient will complete the Functional Assessment of Cancer Therapy –General (FACT-G) prior to protocol treatment

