7.4 Evaluation after Treatment

7.4.1 – Wound complications and late radiation morbidity are reported on appropriate scales. (see section 7.6)

7.4.2 – The patient will complete FACT-G quality of life assessment at 12, 18, and 24 months from the start of radiation treatment

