7.8 Musculoskeletal Tumor Rating Scale (MSTS)

7.8.1 – The MSTS³⁰ is a measure of physical function across 7 items, completed by the physician (preferably by the orthopedic surgeon or Surgical Oncologist) or the physician's designated staff. The 7 items are: pain, range of motion, strength, joint stability, joint deformity, emotional acceptance, and overall function. Each item is scored from 0-5 with a maximum possible score of 35. The MSTS has been in use for over 20 years and is a widely recognized and utilized tool used to evaluate physical function. The MSTS can be completed in approximately 10 minutes by a clinician familiar with the rating. The MSTS rating will be performed at the following time points: prior to start offing on protocol (baseline), and at 12, 18, and 24 months after start of proton radiation therapy.

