8.0 Statistical considerations

8.1 Study endpoints

8.1.1 – Primary endpoint – To determine the effect of reduced radiation volume with proton radiotherapy on combined late radiation toxicities (>grade 2 lymphedema, subcutaneous fibrosis, and joint stiffness) at 2 years from the start of radiation treatment using EORTC/RTOG criteria. See section 7.6.3-7.6.4.

8.1.2 – Secondary endpoints

- 8.1.2.1 – To estimate the effect of reduced radiation volume with proton radiotherapy on late radiation morbidity at 2 years from start of radiation treatment using CTCAE, v.4.0 criteria.
- 8.1.2.2 – Other CTCAE, v.4.0 grade 3-5 events
- 8.1.2.3 – To determine pattern of first failure
- 8.1.2.4 – Time to local failure
- 8.1.2.5 – Time to regional failure
- 8.1.2.6 – Time to distant failure
- 8.1.2.7 – Distant-disease free survival (distant failure or death due to any cause).
- 8.1.2.8 – Disease free survival (local, regional or distant failure or death due to any cause)
- 8.1.2.9 – Overall survival (death due to any cause)
- 8.1.2.10 – Time to second primary tumor
- 8.1.2.11 – Estimate the rate of wound complications
- 8.1.2.12 – To assess the impact of late radiation morbidity at 2 years on clinical measure, MSTS
- 8.1.2.13 – To correlate late radiation morbidity at 2 years with quality of life assessment, FACT-G
- 8.1.2.14 – Estimate the rate of tumor necrosis

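### The FACT-G and MSTS endpoints name no use for the baseline scores the trial already collects; a baseline-adjusted regression on graded morbidity should be specified

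*Combined protocol and SAP*

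**What the plan says.** Section 8.1.2 of the combined protocol and SAP gives one line to each scale. For quality of life (8.1.2.13) it is "To correlate late radiation morbidity at 2 years with quality of life assessment, FACT-G". For function (8.1.2.12) it is "To assess the impact of late radiation morbidity at 2 years on clinical measure, MSTS". Objective 2.2.5 repeats the FACT-G aim but refers to the *degree* of late morbidity. The closing paragraph of the Introduction also speaks of an impact on quality of life.

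Both scales have a pre-treatment value. Section 7.2.1 says the physician or designee "will complete the Musculoskeletal Tumor Rating Scale (MSTS) prior to treatment", and 7.2.2 asks the patient for FACT-G before protocol treatment. Section 7.8.1 repeats MSTS "at 12, 18, and 24 months after start of proton radiation therapy". Section 7.4.2 does the same for FACT-G: "The patient will complete FACT-G quality of life assessment at 12, 18, and 24 months from the start of radiation treatment".

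No model, coefficient, covariate or change score is given for either endpoint. In both lines the 2-year time point attaches to the morbidity, so it is open which later score enters. The only mention of pre-treatment data in section 8 is as a descriptive item in the interim reports (8.3.1.2).

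**The concern.** Patients with and without late toxicity are not randomised groups, so nothing in the design makes them alike before treatment. The documents supply part of a confounding path. The Introduction reports that larger fields predicted more late effects, and 6.4.3 builds the target volume outward from the gross tumor. If larger tumors also went with poorer function or quality of life at entry, low 24-month scores could be attributed to late toxicity when they were partly present from the start.

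The point is sharper for MSTS. Section 7.8.1 lists pain and range of motion among its items, and Table 1 in 7.6.3 uses the same two features to grade joint stiffness. The toxicity row of the table in 7.1 has no pre-treatment entry. Baseline MSTS is therefore the only scheduled scale that the protocol describes as scoring pain and range of motion before treatment.

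At stake are the credibility of the word *impact* and the precision of two secondary estimates in about 41 patients.

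**Working it through.** **Inputs from the documents (8.2).** Evaluable 41, total 51, reference toxicity rate 37%, target 37% − 20 points = 17%. No figure is given for the FACT-G or MSTS analyses.

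**The plan's own figure.** The one-sample score formula, one-sided 0.05 and 90% power, gives [1.645·√(0.37·0.63) + 1.282·√(0.17·0.83)]² / 0.20² = 40.67, so 41. Inflation gives 41/0.80 = 51.25 or 41/(0.95·0.85) = 50.77, in line with 51. The side of the test is not stated; that is a separate matter. Here 41 serves only as the number of patients available.

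**Assumptions.** The SDs of the scores and the within-group baseline-to-24-month correlation r are not in the documents. I work in SD units, with the same SD at both times, and take r = 0.3, 0.5 and 0.7. A two-group contrast stands in for the graded analysis. Toxic patients: 41 × 0.17 ≈ 7 (against 34) or 41 × 0.37 ≈ 15 (against 26).

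**1. Precision, groups alike at baseline.** Unadjusted SE = √(1/k + 1/m): √(1/7 + 1/34) = 0.415 and √(1/15 + 1/26) = 0.324. With baseline as covariate, multiply by √(1 − r²). The difference detectable with 80% power (two-sided 0.05) is (1.96 + 0.84) × SE.

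| r | Variance factor 1 − r² | Variance cut | Detectable, 7 v 34 | Detectable, 15 v 26 |
|---|---|---|---|---|
| unadjusted | 1 | – | 1.16 SD | 0.91 SD |
| 0.3 | 0.91 | 9% | 1.11 SD | 0.87 SD |
| 0.5 | 0.75 | 25% | 1.01 SD | 0.79 SD |
| 0.7 | 0.51 | 49% | 0.83 SD | 0.65 SD |

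**2. Precision, groups different at baseline.** A baseline gap of d SD adds about d²/(41 − 2) to 1/k + 1/m in the adjusted variance. For d = 0.8 that is 0.64/39 = 0.0164, against 0.1723 (7 v 34) or 0.1051 (15 v 26), an inflation of 1.095 or 1.156. The net variance factor is then:

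- r = 0.3: 0.91 × 1.095 = 1.00, or 0.91 × 1.156 = 1.05 (no gain, or a small loss)
- r = 0.5: 0.75 × 1.095 = 0.82, or 0.75 × 1.156 = 0.87
- r = 0.7: 0.51 × 1.095 = 0.56, or 0.51 × 1.156 = 0.59

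**3. Bias if baseline is left out.** With no true effect, a baseline gap of d leaves a 24-month difference of r·d. For d = 0.5 this is 0.15, 0.25 and 0.35 SD. An unadjusted nominal 5% test then rejects 6.5%, 9.2% and 13.5% of the time with 7 v 34, and 7.5%, 12% and 19% with 15 v 26.

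**4. Covariate or change score.** A raw change score has variance factor 2(1 − r): 1.4, 1.0 and 0.6 at the three values of r. It is worse than the unadjusted score below r = 0.5, and worse than the covariate (0.91, 0.75, 0.51) throughout this range.

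**5. Grade or yes/no.** If severity is an underlying normal variable, splitting it so that a fraction p is toxic keeps φ(z_p)²/[p(1 − p)] of the information: about 45% at 7/41 and 61% at 15/41. A grade from 0 to 4 also loses something, so these overstate the cost of the split relative to the grade. At r = 0.5 the covariate is worth a factor of 1/0.75 = 1.33, and 0.45 × 1.33 = 0.60 and 0.61 × 1.33 = 0.81 are both below 1. On that bound, the yes/no split can cost more than the covariate gains.

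**The case against.** The strongest reply is that the plan has not chosen a wrong analysis; it has stated two aims and no analysis. A reader might infer that the plan prescribes a comparison of 24-month scores that ignores baseline, so that pre-existing differences will be read as late morbidity. The documents do not support this. They fix no score time point, they do not exclude baseline, and 7.8.1 itself labels the pre-treatment MSTS as baseline.

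Confounding is not shown either. It needs baseline scores that differ by later toxicity and that predict later scores, and the documents give data on neither. No section links tumor size to baseline MSTS or FACT-G, and entry is limited to ECOG 0-1 (3.1.5), which may narrow the baseline range. The precision gain rests on an assumed correlation and shrinks if the groups differ at baseline. Nor does adjustment deliver an effect of morbidity: it leaves the extent of surgery and the overlap between MSTS items and joint-stiffness grading in place.

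All of this stands, and it limits the point without removing it. Followed as written, the FACT-G line is a raw correlation. The plan collects what is needed for a better analysis and does not commit to using it, which leaves the choice open until the data are seen.

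**Conclusion.** The point holds as a weakness of two secondary endpoints: the method, the score time point and the role of baseline are unstated, and the literal reading is weaker than the collected data allow. Under r = 0.3 to 0.7 and little baseline difference between toxicity groups, adjustment cuts residual variance by 9% to 49%; the gain is small at r = 0.3 and can vanish there if the groups differ. Bias is conditional: a 0.5 SD baseline gap would leave a spurious 0.15 to 0.35 SD, but whether any gap exists is unknown.

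It would go too far to call the present plan biased, to call the remedy free, or to replace graded morbidity with a yes/no contrast as the main analysis. That last step would depart from objective 2.2.5. The importance is low: the primary test, the 41 evaluable patients and the total of 51 are untouched.

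**What to change.** Add to 8.1.2.12 and 8.1.2.13 text to this effect:

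> The 24-month FACT-G score, and separately the 24-month MSTS score, will be regressed on the degree of late radiation morbidity at 2 years (for example the worst grade, 0 to 4, across lymphedema, fibrosis and joint stiffness), with the corresponding baseline score as covariate. The adjusted estimate will be reported with its confidence interval.

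Three supporting points belong with it:

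- Keep the raw correlation as a descriptive result, and the contrast of grade 2 or greater against lower grades as a supplementary summary.
- Use baseline as a covariate, not a change score.
- State that the result is an association, because adjustment does not account for the extent of surgery or for the shared content of MSTS and joint-stiffness grading.

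The cost is one degree of freedom in each model and reliance on a completed baseline form. No new data or visits are needed.

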8.2 Overview and Sample size

8.2.1 – This prospective study is designed to assess late radiation toxicity. The primary endpoint is whether or not a patient experiences at least 1 of the 3 toxicities at a severity of grade 2 or greater at 2 years from start of radiation treatment. The NCIC study showed 31.5% grade 2 or greater fibrosis, 15.1% lymphedema and 17.8% joint stiffness in the preoperative arm at 2 years following treatment, and 37% of patients had at least one of these 3 toxicities at 2 years.

8.2.2 – We will test for a 20% absolute decrease in combined toxicity. A sample size of 41 patients is required to show a 20% decrease with a significance level of 0.05 and 90% power. Assuming that 5% of patients will be retrospectively ineligible and an additional 15% will not have a 2-year assessment for the primary endpoint due to death or loss to follow up, the total targeted sample size in this study is 51 patients.

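### Section 8.2.2 names no test, sidedness or success cut-off, and at 41 evaluable patients no cut-off gives both a 0.05 significance level and 90% power

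*Combined protocol and SAP*

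**What the plan says.** Section 8.2.1 defines a binary endpoint, "whether or not a patient experiences at least 1 of the 3 toxicities at a severity of grade 2 or greater at 2 years", and takes its historical comparator from the preoperative arm of the NCIC trial, where "37% of patients had at least one of these 3 toxicities at 2 years". Section 8.2.2 then says "We will test for a 20% absolute decrease in combined toxicity" and sizes the trial: "A sample size of 41 patients is required to show a 20% decrease with a significance level of 0.05 and 90% power". Two allowances raise enrolment to 51. One is 5% for patients later found not to qualify; the other is that "an additional 15% will not have a 2-year assessment for the primary endpoint due to death or loss to follow up".

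Nothing else in the document describes how the primary endpoint will be tested. Section 8.1 lists endpoints and section 8.3 covers safety monitoring and interim reports. The test, its sidedness and the success count are not given anywhere.

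**The concern.** This is a single-arm study judged against a published rate. Without a concurrent control, a decision rule fixed in advance is the main protection against choosing the analysis after seeing the result. Here there is no such rule.

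The gap matters because the sample is small and the endpoint is a count. With about 41 patients, one patient more or fewer moves the p-value across 0.05, and reasonable tests place the boundary at different counts. The stated pair of 0.05 and 90% may also not be what any actual rule delivers at 41. If so, the plan misdescribes its own operating characteristics, and a result near the boundary could be called a success or a failure depending on the test picked.

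**Working it through.** **Inputs.** Null rate p0 = 0.37 (8.2.1). Alternative p1 = 0.37 − 0.20 = 0.17 (8.2.2; the figure 17% is derived, not written). Alpha 0.05, power 0.90, 41 evaluable, 51 enrolled, losses of 5% and 15% (all 8.2.2). Assumed: a one-sample test against a fixed 37%.

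**1. Reproducing 41.** One-sided, one-sample normal approximation:

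n = [(1.645·√(0.37·0.63) + 1.282·√(0.17·0.83)) / 0.20]² = [(0.794 + 0.481) / 0.20]² = 40.67, rounded up to 41.

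The two-sided version gives 50.96, so 51. Two independent arms would need 83 per arm one-sided. The stated 41 therefore points to a one-sided, one-sample, large-sample calculation. Enrolment also reproduces: 41/(0.95 × 0.85) = 50.8, so 51.

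**2. Exact error rates at 41.** With X the number of patients with the endpoint and success declared when X ≤ c:

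| c | alpha = P(X ≤ c), rate 37% | power = P(X ≤ c), rate 17% |
|---|---|---|
| 8 | 0.0127 | 74.6% |
| 9 | 0.0300 | 85.3% |
| 10 | 0.0624 | 92.3% |
| 11 | 0.116 | 96.4% |

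Alpha and power both rise with c, so no cut-off has alpha at or below 0.05 together with power of at least 90%. With c = 9, power reaches 90% only if the true rate is about 15.7%.

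**3. Where the tests disagree at 41.** At 10/41 (24.4%), z = (0.2439 − 0.37)/√(0.37·0.63/41) = −1.67, one-sided p = 0.047, a success. The exact p-value is 0.062, a failure. The probability of exactly 10/41 is 7.0% at a true rate of 17% and 3.2% at 37%.

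Sidedness adds to this. If 0.05 were two-sided with 0.025 in the lower tail, the exact cut-off would be 8/41 with power 74.6%, and 9/41 (lower-tail p = 0.030) would also fail.

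**4. Other evaluable numbers.** One-sided 0.05, exact cut-off against z cut-off, from 36 to 46 evaluable:

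| n | exact c | z c | exact power |
|---|---|---|---|
| 38 | 8 | 9 | 81.4% |
| 41 | 9 | 10 | 85.3% |
| 42 | 9 | 10 | 83.5% |
| 44 | 10 | 11 | 88.5% |
| 45 | 10 | 11 | 86.9% |

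The cut-offs coincide at 36, 37, 39, 40, 43 and 46. At 39, 43 and 46 the exact power is 88.6%, 89.9% and 92.1%.

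**5. Averaging over the evaluable number.** If each of 51 patients independently has an 80% chance of being evaluable (an assumption built from the 5% and 15%):

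| Test | average true alpha | average power |
|---|---|---|
| One-sided exact | 0.034 | 86.1% |
| One-sided z | 0.0496 | 89.8% |

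On the same assumption, the chance that the two tests reach opposite conclusions is the difference between rows: 89.8% − 86.1% = 3.7% at a true rate of 17%, and 0.0496 − 0.034, about 1.5%, at 37%.

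**The case against.** The strongest reply is that this is ordinary discreteness. Every binomial design moves in a saw-tooth around its nominal values, and 41 is an unfavourable point for the z-test. The plan does not promise exactly 41 evaluable patients, and on the 80% assumption exactly 41 occurs about 14% of the time. Averaged over the evaluable number, the z-test, the kind of large-sample method that reproduces the plan's 41, essentially meets the stated 0.05 and 90%. The two tests then disagree only 3.7% or 1.5% of the time, about half the figures for exactly 41. A large-sample or mid-p test (mid-p at 10/41 is 0.046) is a defensible choice. One-sidedness can be inferred from the word decrease and from 41 itself.

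Much of this stands. The 41 is not an error, the shortfall is modest, and the averaged figures are the fairer guide to how often the conclusion would change. It does not close the gap, because the plan names neither the z-test nor any other, and an inference about sidedness does not bind the analyst. At the number the plan itself states, neither the exact test nor the z-test delivers both properties.

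**Conclusion.** The concern holds. Section 8.2.2 leaves the test, sidedness and cut-off open, and its stated pair of error rates is not achieved by any count-based rule at 41. The size is modest: 4.7 points of power (85.3% against 90%) with a cut-off of 9, or 1.2 points of alpha (0.062 against 0.05) with a cut-off of 10. The practical risk is a borderline result, 10/41 above all, whose interpretation is not settled in advance.

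This rests on a one-sided, one-sample comparison with a fixed 37% and an alternative of 17%. The averaged figures also assume an independent 80% chance of being evaluable. It should be fixed before the 2-year outcomes are analysed.

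**What to change.** Add to 8.2.2 wording such as: *One-sided exact binomial test of H0: 2-year rate at least 37%, alpha 0.05. With 41 evaluable patients, success is 9 or fewer with the endpoint (actual alpha 0.030); power is about 85% at a true rate of 17%. If the evaluable number is not 41, the cut-off is the largest count with exact alpha no greater than 0.05 at that number.* Note beside it that power varies with the evaluable number.

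If the sponsor prefers the z-test, name it and state its cut-off of 10/41 and true alpha of 0.062.

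Either version is wording only and needs no extra patients. The price is that stated power falls from 90% to about 85%, or stated alpha at 41 rises to 0.062. If both original targets must hold exactly, the smallest evaluable number is 46 (11 or fewer: alpha 0.043, power 92.1%). That means 46/(0.95 × 0.85) = 57 enrolled, six more than planned, and power would still vary with the evaluable number (89.7% at 48).
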